4.6.4 Electrocardiogram (ECG)

Standard 12-lead ECG parameters (PR, RR, QRS, QT, QTcF and HR) and ECG abnormal assessment will be listed for individual subjects.

[figure not shown]
For each ECG variable, baseline value will be calculated from the means of the available data prior to dose, if multiple values are recorded. Change from baseline values will be calculated as the assessment values minus baseline values.

Descriptive statistics will be calculated for absolute value of each parameter, together with the corresponding changes from baseline overall and by dose and timepoint. Where multiple values are recorded at a timepoint for a subject, the mean of the available values will be used in the summary statistics.

4.6.5 Physical examination

A summary table will be produced for each physical examination test reporting PI interpretation category (n and %) by cohort, timepoint and arm.

Physical examination data will be listed for individual subjects.

4.6.6 Neurological examination

A summary table will be produced for each neurological examination test reporting PI interpretation category (n and %) by cohort, timepoint and arm.

Neurological examination data will be listed for individual subjects.

4.7 SAFETY REVIEW COMMITTEE

SRC analysis is out of scope of this SAP and details are contained within the SRC charter.

5 HANDLING OF MISSING OR INCOMPLETE DATA

Unrecorded values will be treated as missing. Efforts will be made to prevent this from occurring. For complete missing visits the missing efficacy, safety will be treated as missing at random and will not be imputed in the statistical analysis except for partial dates.

For the exploratory efficacy analysis, frequency of missing data will be reported in a separate table as described within the analysis section.

5.1 PRIOR AND CONCOMITANT MEDICATION DATES

Partial dates for any prior and concomitant medications recorded in the eCRF will be imputed using the following convention:

- If the partial date is a start date, a '01' will be used for the day and 'Jan' will be used for the month.
- If the partial date is a stop date, a '28/29/30/31' will be used for the day (dependent on the month and year) and 'Dec' will be used for the month.

The recorded partial date will be displayed in listings. No imputation will be performed for completely missing start and end dates.

5.2 AE START AND END DATES

The eCRF allows for the possibility of partial dates (i.e. only month and year) to be recorded for AE start and end dates; that is the day of the month may be missing. In such a case, the following conventions will be applied for calculating the time of onset and the duration of the event:

- Missing Start Day: First of the month will be used unless this is before the start date of first study treatment; in this case the study treatment start date will be used and hence the event is considered treatment emergent.
- Missing Stop Day: Last day of the month will be used, unless this is after the stop date of study completion; in this case the study stop date will be used.

Completely missing start or end dates will remain missing, with no imputation applied. Consequently, time to onset and duration of such events will be missing.

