Subjects will be required to attend the CRU for a Screening visit within 28 days prior to first dosing to ensure they meet the inclusion/exclusion criteria and are in good health. Subjects will be admitted to the CRU 1 day prior to first dosing (Day -1) for collection of baseline safety assessments and will receive their first dose of ivermectin or placebo in the morning of Day 1, following an overnight fast. Subsequent daily doses of ivermectin or placebo will be administered in the morning in the CRU from Day 2 to Day 7, following an overnight fast. Subjects will reside in the CRU until at least 4 hours post-dose on Day 7 for the collection of safety assessments and PK blood samples but may reside for longer if deemed necessary by the Investigator. From Day 8 to Day 27, subjects will self-administer their daily dose of ivermectin or placebo at home following an overnight fast, with the exception of outpatient visits on Day 14 and Day 21 which will be administered in the CRU. Subjects will be readmitted to the CRU on Day 28 to receive their final dose of ivermectin or placebo and will be discharged on Day 29 following safety assessments and PK blood samples. Subjects will return to the CRU for outpatient visits on Days 32, 35 and 42 for safety assessments and PK blood samples.

A detailed plan of study assessments is provided in [Appendix 1](#).

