7.6.3. Reporting Procedures and Requirements

7.6.3.1. Adverse Events

Events meeting the criteria in [Section 7.6.1.1](#) occurring from the time of signed informed consent will be considered as AEs. All AEs between Screening to the Follow-up visit will be recorded in source and eCRF, whether or not considered study medication related. All AEs that are possibly or probably related to study medication will be followed until resolution or database lock, whichever occurs first. Also, the sign, symptom, or disease present before the baseline AE assessment are only considered AEs if they worsen after this point. Any AEs already documented at a previous assessment and designated as ongoing should be reviewed at subsequent visits as necessary. If these have resolved, this should be documented. Changes in intensity or frequency of AEs should be recorded as separate events (i.e., a new record started). The Investigator should report all AEs on the AE page(s) of the eCRF and source documents, regardless of seriousness, severity, and causality. Whenever possible, an AE will be reported using a diagnostic term, (e.g., “common cold” or “upper respiratory infection” rather than “runny nose, cough, mild fever”) and should be described with the attributes described in [Section 7.6.1.1](#).

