12. DATA HANDLING AND RECORD KEEPING

12.1. Collection of Data

Data collected from each completed subject will be recorded on source documents, which will be entered into an eCRF. The Investigator is responsible for ensuring that all sections of the eCRF are completed correctly and that entries can be verified against the source documents. If certain data are not available or not applicable this will be indicated as such within the appropriate area of the eCRF.

Screening failures (subjects who signed consent to take part in the study but were not dosed) will not be entered into the clinical study database.

Data produced by automatic devices with original printouts (i.e., clinical laboratory evaluation results, ECG traces) will be attached to the source documents. Clinical laboratory parameters will be provided in laboratory printouts which are to be signed by the Investigator. Comments on all clinically significant abnormal values will be provided and documented by the Investigator or appropriately recorded within the eCRF.

Adverse Events and Medical History will be reported by the MedDRA SOC and PT; the latest version will be applied to all terms. All Medical History and AEs will be included in the data listings. Furthermore, all Prior Medications and Concomitant Medications will be reported using the WHODRUG categorization; the latest version will be applied to all terms.

All Prior Medications and Concomitant Medications will be summarised within the data listings.

Any missing, implausible or inconsistent recordings within the eCRFs will be referred to the Investigator using data query validation procedures; will be documented and resolved for each individual subject before database lock is declared.

All processes pertaining to the Data Management activities will be detailed within the Data Management Plan.

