4.6.1 Adverse Events

Adverse events will be listed in the following categories:

 Treatment-emergent adverse events (TEAEs) are any AEs with a start date and time on or after dosing with ivermectin/placebo. All TEAEs will be listed and summarised as indicated below

The overall incidence of TEAEs (number and percentage of subjects) as well as the number of events will be summarised by treatment, cohort and overall, categories of degree of severity, serious adverse events (SAEs), causally related TEAEs and SAEs, TEAEs leading to discontinuation of treatment and AEs or SAEs leading to withdrawal.

TEAEs will be summarised at both the subject [number (%) of subjects] and event [number of events] level for the following:

- System Organ Class (SOC) and PT
- SOC and PT and maximum reported severity
- SOC and PT and causal relationship to study drug

These analyses will be repeated for SAEs and treatment related AE if deemed necessary, otherwise only the SAEs by SOC and PT will be performed.

For the incidence at the subject level by SOC and PT; if a subject experiences more than one event within the same SOC and PT, only one occurrence will be included in the incidence.

For the incidence at the subject level by SOC, PT and severity; if a subject experiences more than one event within the same SOC and PT, only the most severe occurrence will be included in the incidence.

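### SAP 5.2 makes every adverse event with a missing start day treatment emergent, even when its recorded month or stop date is before first dose

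*SAP*

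**What the plan says.** SAP 5.2 deals with AE dates for which month and year are recorded and only the day is missing. For a start date, "First of the month will be used unless this is before the start date of first study treatment". When the first of the month does fall before first treatment, "in this case the study treatment start date will be used and hence the event is considered treatment emergent". For a stop date, "Last day of the month will be used, unless this is after the stop date of study completion", in which case the study stop date is used. These imputed dates feed time to onset and duration.

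SAP 4.6.1 defines TEAEs as "any AEs with a start date and time on or after dosing with ivermectin/placebo". It reports them as subjects (n and %) and as events, by treatment, cohort and overall.

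Two protocol provisions allow AEs before dosing to be in the data. In section 7.6.3.1, events "occurring from the time of signed informed consent will be considered as AEs". In section 3, "Subjects will be required to attend the CRU for a Screening visit within 28 days prior to first dosing".

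**The concern.** Moving a start to the first-dose date is the usual conservative choice when the event began in the dosing month and could have begun on either side of the dose. SAP 5.2 goes further. The first of any earlier month always precedes first treatment, so the exception also applies to events whose recorded month shows that they began before dosing. It then overrides known information and conflicts with the TEAE definition in SAP 4.6.1.

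The stop date has no role in the start rule. An event known to have ended before first dose can be given a start after its end, so the two bullets of SAP 5.2 can contradict each other.

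At stake are the TEAE counts and percentages, which can only be inflated by this rule (in either arm), and the onset and duration of the affected events. Safety is the secondary objective, and the cohort cells are small.

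**Working it through.** The plan gives no figure to reproduce. The check applies the rule as written to test cases and then sizes one misclassification.

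**1. Which recorded months can escape TEAE status?**
- Earlier than the first-dose month: the first of that month precedes first dose, so the start becomes the first-dose date; TEAE.
- Same month: the first of the month is on or before the first-dose date, so the start is the first-dose date; TEAE.
- Later month: the first of that month is after first dose; TEAE.

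No missing-day start can be classed as not treatment emergent.

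**2. Test cases.** Assumed dates: consent 20 January, first dose 10 February. The last two columns apply the rule set out under the fix.

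| Recorded start | Stop | SAP 5.2 start | SAP 5.2 class | Stop minus start | Replacement start | Replacement class |
|---|---|---|---|---|---|---|
| January | January (imputed 31 Jan) | 10 Feb | TEAE | −10 days | 20 Jan | not TEAE |
| February | 5 Feb | 10 Feb | TEAE | −5 days | 1 Feb | not TEAE |
| February | none | 10 Feb | TEAE | – | 10 Feb | TEAE |
| March | any consistent date | 1 Mar | TEAE | ≥ 0 | 1 Mar | TEAE |

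The first two rows are wrong under SAP 5.2. The last two are unaffected.

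**3. Can the situation arise?** Take Day 1 dates spread evenly over 2021 and a consent-to-dose interval of k days, with k at most 28 (assumptions). A Day 1 on day D of a month has max(0, k − (D − 1)) of its k pre-dose days in an earlier month. Summed over a month this is k(k + 1)/2, so the average share is

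12 × [k(k + 1)/2] / (365 × k) = 6(k + 1)/365.

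- k = 7: 48/365 = 13%
- k = 14: 90/365 = 25%
- k = 21: 132/365 = 36%
- k = 28: 174/365 = 48%

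A full 28-day window reaches an earlier month for 12 × 28 = 336 of 365 Day 1 dates (92%). These figures show that pre-dose AEs in an earlier month are possible. They are not error rates.

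**4. Size of one misclassified subject.** SAP 1.4 plans 6 ivermectin and 2 placebo subjects in each of 3 cohorts. If the subject has no other TEAE in that category:
- ivermectin cohort cell: 1/6 = 16.7 points
- placebo cohort cell: 1/2 = 50 points
- pooled ivermectin: 1/(3 × 6) = 1/18 = 5.6 points
- pooled placebo: 1/(3 × 2) = 1/6 = 16.7 points

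If the subject already has a TEAE in that category, incidence does not change and the event count rises by 1.

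**The case against.** The strongest reply is that the bullet only supplies a missing day, so it should be read as confined to the first-dose month. There it is conventional, and SAP 4.6.1 would separately keep out an event recorded in an earlier month. That may be what was meant, but the text does not say so. A programmer following it would produce the results above. The narrower reading also leaves the second test case unresolved, where the event starts in the dosing month and ends before the dose.

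The second reply is rarity. The error needs a new AE between consent and dosing, in a subject later dosed, with the start day unknown, and either an earlier recorded month or a stop before first dose. Protocol 12.1 provides that "Any missing, implausible or inconsistent recordings within the eCRFs will be referred to the Investigator" and resolved before lock. Protocol 11.6 reassesses missing-data methods before lock. Protocol 7.6.3.1 counts a condition present before the baseline AE assessment only if it worsens afterwards. If that assessment is the one nearest dosing, many such records would not be AEs at all; the consent clause in the same section points the other way. All of this reduces how often the rule is used. None of it corrects the rule's output for the dates that remain partial, which are the ones SAP 5.2 exists to handle.

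The third reply is consequence, and it largely stands. Safety is descriptive with no hypothesis tests, and the Safety Review Committee's analysis is outside this SAP. An event that began before dosing is also unlikely to be judged drug related.

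**Conclusion.** The concern holds. As written, SAP 5.2 makes every AE with a missing start day treatment emergent, including those whose recorded month or stop date places them before dosing. This contradicts SAP 4.6.1 and can give a start after the stop.

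The rule's logic is certain, but its effect on the reported tables is not. The number of affected records is not given, is probably low, and may be zero. If one subject is affected and has no other TEAE in that category, the shift is 16.7 or 50 points in a cohort cell and 5.6 or 16.7 points pooled, for ivermectin and placebo respectively. The direction is always towards over-counting. The same-month case with no contradicting stop date is sound and should be kept.

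**What to change.** Replace the missing-start-day bullet in SAP 5.2 with:

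- **(a)** Recorded month and year equal those of first dosing, and the stop date (recorded, or imputed by the stop-day rule) is missing or not before first dose: use the first-dose date; treatment emergent.
- **(b)** Recorded month earlier than the first-dose month, or event stopped before first dose: use the first of the recorded month, or the consent date if that is later in the same month; not treatment emergent.
- **(c)** Recorded month later than the first-dose month: use the first of that month; treatment emergent.
- **(d)** Never impute a start after the stop date; if one would result, use the stop date.

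A record whose start month is later than its stop date can meet both (b) and (c), or trigger (d). It is internally inconsistent and should go to data query under Protocol 12.1 before any imputation. Among records that agree internally, (a) to (c) do not overlap.

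Post-dose worsening is not lost under (b), because Protocol 7.6.3.1 states that "Changes in intensity or frequency of AEs should be recorded as separate events", each with its own start.

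The cost is SAP wording and a few lines of code, with no new data and no change in trial conduct.

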7. SAFETY ASSESSMENTS

Baseline safety data assessments for all parts of the study will be collected pre-dose at the nearest timepoint to dosing as shown in [Appendix 1](#). The subjects will attend a Follow-up visit 14 days after the final dose for safety follow-up procedures

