7.6.3.2. Serious Adverse Events

Each AE will be assessed to determine whether it meets seriousness criteria ([Section 7.6.1.2](#)). If the AE is considered serious the Investigator should report this event to the Sponsor. The Sponsor will report the event to the research ethics committee (REC) according to its SOPs. Serious adverse events occurring from the time of signed informed consent to the follow-up visit or 7 days after the last dose of study medication (whichever occurs later) will be recorded in source and electronic data capture; ongoing SAEs after this time frame will be followed until the Investigator, Medical Monitor, and Sponsor agree that the SAE is satisfactorily resolved, or stably unresolved. Serious adverse events considered by the Investigator to be related to study medication, regardless of the time of onset after treatment, should be reported. All information about SAEs will be collected and reported via the SAE form and sent by email message (contact information will be contained in the Investigator site file). The Investigator should send the initial report within 24 hours of becoming aware of the SAE. At a minimum, the initial report should include the following information:

- Event
- Seriousness criteria
- Protocol number
- Subject number, initials and date of birth
- Study medication
- Reporter name and contact information

In the case of a “minimum report” (one that solely comprises the information bulleted above), a more detailed follow-up report should be sent as soon as more information becomes available but no later than 7 calendar days after the date of the initial report. Each SAE should be followed up until resolution or stabilisation and for reported deaths, the Investigator should supply MedinCell or its designee and the REC with any additional requested information (e.g., autopsy reports and terminal medical reports), if available. The original SAE form should be kept at the study site. The Investigator will be responsible for determining and in turn, reporting SAEs to the Sponsor. MedinCell or its designee will be responsible for reporting SAEs to regulatory authorities according to the applicable regulatory requirements. MedinCell or its designee will be responsible for completing the safety report and for notifying the relevant authorities of any SAE as outlined in the International Council for Harmonisation (ICH) Guidelines and per local regulatory requirements.

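### The SAP 5.2 cap on partial AE stop dates can place the end of an event before its recorded month begins (minor; derived durations only)

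*SAP*

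**What the plan says.** **Imputation rule (SAP 5.2).** The section deals with incomplete AE dates: "The eCRF allows for the possibility of partial dates (i.e. only month and year) to be recorded for AE start and end dates". Its stated purpose is that "the following conventions will be applied for calculating the time of onset and the duration of the event". For the end of an event the rule is: "Missing Stop Day: Last day of the month will be used, unless this is after the stop date of study completion". Where that exception applies, the date on which the study stopped is substituted. The rule does not require the substituted date to fall in the recorded month or after the event began. Dates that are wholly missing stay missing.

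**Follow-up of events (protocol).** Three provisions allow an event to be followed after a subject's last scheduled visit:
- Section 7.6.3.1, related AEs: "All AEs that are possibly or probably related to study medication will be followed until resolution or database lock, whichever occurs first".
- Section 7.6.3.2, SAEs whatever their cause: "ongoing SAEs after this time frame will be followed until the Investigator, Medical Monitor, and Sponsor agree that the SAE is satisfactorily resolved". The same section adds, on late onset: "Serious adverse events considered by the Investigator to be related to study medication, regardless of the time of onset after treatment, should be reported".
- Section 7.1, laboratory results: clinically significant values are tracked until they resolve or stabilise, with no causality condition. Section 7.6.1.3 records such findings as AEs when they meet the AE definition.

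**Completion.** SAP 5.2 does not define study completion. Protocol section 7 says "The subjects will attend a Follow-up visit 14 days after the final dose for safety follow-up procedures", which is Day 42 for the subject. Section 14.4 defines the end of the study by the last subject's follow-up visit.

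**The concern.** An imputation rule should fill in what is unknown and leave alone what is known. Here the day is unknown and the month is known. The cap is reasonable for events whose observation ends at the last visit, but the protocol expects some events to have stop dates later than that. For those events the rule overwrites a recorded month with an earlier date.

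At stake is the derived duration of AEs that persist past completion. Safety and tolerability form the secondary objective, and in a study this small each persistent event is likely to be read individually. A duration cut off at completion would make a lingering event look shorter than the record shows.

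**Working it through.** The plan gives no figure on this point, so there is none to reproduce. The check is to apply the rule to dates and compare the result with what the recorded month allows.

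**Definitions.** C = completion date; F and L = first and last day of the recorded stop month; duration = stop − onset + 1.

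Rule in SAP 5.2: imputed stop = the earlier of L and C.

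**General result.** If the recorded month is later than the completion month, then C < F ≤ L. The rule therefore always returns C, a date before the recorded month begins. The stop is too early by at least F − C days and at most L − C days. If the recorded month is the completion month, C lies inside it and the recorded month is not contradicted.

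**Worked case.** Calendar dates are assumed. Day 1 = 4 January 2021, so Day 42 = 14 February 2021 (4 January + 41 days), taken as C. Onset on Day 20 = 23 January. From 23 January to 14 February inclusive is 9 + 14 = 23 days.

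| Recorded stop | Imputed stop | Duration by the rule | Duration the record allows |
|---|---|---|---|
| February 2021 | 14 February | 23 | 10 to 37 |
| March 2021 | 14 February | 23 | 38 to 68 |
| April 2021 | 14 February | 23 | 69 to 98 |
| June 2021 | 14 February | 23 | 130 to 159 |

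For March, the lower bound is 9 + 28 + 1 = 38 and the upper bound is 9 + 28 + 31 = 68. The rule's 23 days is 61% of the shortest possible duration (23/38) and 34% of the longest (23/68). For February the imputed value sits inside the possible range.

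**Other start dates.** Day 1 was set to each date in 2021, with completion on Day 42:

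| Recorded month relative to completion month | Days before its first day (F − C) | Days before its last day (L − C) |
|---|---|---|
| 1 month later | 1 to 31 | 28 to 61 |
| 2 months later | 29 to 62 | 59 to 91 |
| 3 months later | 60 to 92 | 89 to 122 |

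**Onset after completion.** Take a related SAE starting on 6 March 2021 with its stop recorded as March 2021. The rule gives 14 February, which is 20 days before onset, so duration = −20 + 1 = −19 days. Nothing in SAP 5.2 prevents this.

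**If completion means the last subject's visit.** Assume all three cohorts run at the shortest spacing the design allows. The remaining subjects start on the sentinels' Day 8, so their Day 14 falls on day 21 of the cohort and the next cohort can start on day 22. Cohorts then start on study days 1, 22 and 43, and the last subject's Day 42 falls on study day 43 + 7 + 41 = 91. The first sentinel's own Day 42 is study day 42, so the cap comes at least 91 − 42 = 49 days later for that subject. For the last subject dosed the gap is zero. The contradiction remains under this reading, but it mainly affects the last cohort.

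**The case against.** The strongest objection is that no specified analysis uses AE duration. SAP 4.6.1 and protocol 11.5.1.1 plan listings and counts of subjects and events by class, term, severity, causality and seriousness. Treatment-emergent status depends on the start date, so no TEAE count moves. Any display of duration would be in the table shells, a separate document under SAP section 6. This stands, and it limits the consequence.

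The trigger is also rare. It needs a missing stop day and a stop month later than completion, among at most 24 healthy subjects. Events still being followed are under active contact, and protocol 12.1 has missing or inconsistent eCRF entries queried and resolved before lock. This stands too. The documents give no basis for estimating a frequency.

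Three stronger readings are tempting but not supported:
- *The error falls only on drug-related events and SAEs, and so selectively hides drug toxicity.* Protocol 7.1 follows clinically significant laboratory values whatever their cause, and SAEs are followed whatever their causality. Unrelated events can be hit as well.
- *The error falls on the longest events.* A short event that starts near Day 42 and ends in the following month is treated the same way.
- *Listings will show the event as over by study end.* SAP 5.2 ties its conventions to calculating onset time and duration, and SAP 4.1 says listings contain all available data. SAP 5.1 states that recorded partial medication dates will be displayed; SAP 5.2 does not say this for AEs, so the point is open, but the text does not say that imputed dates replace recorded ones.

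None of this makes the rule correct where it applies. SAP 5.2 names duration as the quantity it serves and then gives a value that the recorded month rules out.

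**Conclusion.** The point holds, with minor severity. For an AE whose stop day is missing and whose recorded stop month is later than the completion month, SAP 5.2 always gives a stop date before that month. The duration is then too short: by at least 1 to 31 days when the stop is one month later, and by more for later months. It can be negative for a related SAE that starts after completion.

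The effect is confined to derived AE durations and any listing or shell that shows them. When the recorded month is the completion month, the imputed date stays inside that month.

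The day counts rest on assumed calendar dates and on reading completion as the subject's Day 42. Under the last-subject reading fewer events are affected, though the rule still conflicts with follow-up that runs on to database lock or beyond. The conflict itself rests only on the text of the two documents.

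**What to change.** Replace the stop-day rule in SAP 5.2, for all AEs regardless of causality, with wording such as:

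> Missing stop day: last day of the recorded month, or the date of last contact or database lock if that is earlier and falls within the recorded month. The imputed stop must never fall outside the recorded month or before AE onset.

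Then either drop the study-completion cap, or define study completion (subject's follow-up visit or last subject's follow-up visit) and apply the cap only when the recorded month is the completion month and the event is known to have ended by then. The rule should not depend on relatedness: that would give different durations to related and unrelated events with identical recorded dates, for no gain.

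The cost is a sentence or two in SAP 5.2 and a line of derivation code. No new data are needed. The change should be made before database lock.
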